11.6 SLE Disease Activity Assessment

The specific research instruments that will be used to assess disease activity and quality of life include:

- Chest X-Ray

Chest X-Ray will be obtained where allowed by Local Regulation for SLICC/ACR-DI purpose at Visit 2 (X-Ray obtained within previous month is acceptable) and at Visit 12.

- SLEDAI-2K score (Gladman *et al.*, 2002) - see Appendix 2

The SLEDAI scale measures disease activity. The original version was modified (SLEDAI-2K) to better reflect persistent active disease. There are 24 items in a total of 9 organs/systems; total scores range from 0 (non-active disease) – 105 points. Scores are attributed taking into account disease activity over the previous 10 days.

- BILAG-2004 index (Yee *et al.* 2010) - see Appendix 3

The BILAG 2004 index categorizes disease activity into 5 different levels from A–E, with Grade A representing very active disease and Grade E indicating no current or previous disease activity. Scoring is based on a total of 101 items, grouped into 9 organ/systems. Scores are attributed taking into account the signs/symptoms of SLE occurring over the previous 4 weeks.

- PGA score

PGA score is captured using 100 mm VAS

- SELENA-SLEDAI flare index (Petri *et al.*, 1999; Griffiths, *et al.* 2005) – see Appendix 4

- SLICC/ACR-DI (Gladman *et al.*, 1996) – see Appendix 5

The SLICC/ACR-DI captures permanent changes which have occurred in patients with SLE, regardless of causality. The questionnaire contains 41 items covering 12 different organ systems.

- Count of Tender and Swollen Joints and joint pain VAS – see Appendix 6

Count of Tender and Swollen Joints will be captured with 28-Tender and Swollen Joint counts and Joint pain is captured using 100 mm VAS

- CLASI (Albrecht *et al.*, 2005) – see Appendix 7

The CLASI was specifically developed to assess the cutaneous manifestations of SLE. It measures both disease activity and permanent damage (e.g. dyspigmentation and scarring) over the entire body surface.

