3.3.2 Per-protocol (PP) dataset

The PP population will be a subset of the FAS including all randomized patients having received at least one dose of study product (IFN-K or placebo), and who complied with the procedures defined in the protocol (*i.e.*, who did not have major protocol deviations that could impact the primary endpoint analysis).

In addition, patients with at least one of the following cases will be excluded from the PP population:

- missing IFN gene signature at baseline
- missing IFN gene signature at week 24 and week 36
- missing BICLA at week 36, *i.e.*:
 - all missing BILAG at baseline
 - or missing BILAG at week 36 corresponding to a BILAG A or B at baseline
 - or all missing BILAG at week 36

Statistical Analysis Plan

Study Name: IFN-K-002

SAP version & date: v4, 18/Jun/2018

- or missing SLEDAI-2K at baseline
- or missing SLEDAI-2K at week 36
- or missing PGA on VAS 100 mm at baseline
- or missing PGA on VAS 100 mm at week 36
- less than 4 doses of study product received (out of 5)

This will also be the population used for the immunogenicity, autoantibodies and biomarkers analyses.

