4.1 Efficacy endpoints

4.1.1 Primary efficacy endpoint(s)

Two co-primary endpoints are evaluated in the trial:

- Change from baseline in the expression of IFN-induced genes at Week 36.
- Response to treatment with IFN-K as measured by the British Isles Lupus Assessment Group (BILAG)-based Composite Lupus Assessment (BICLA) response criteria at Week 36:
 - All BILAG A scores at baseline improve to B/C/D and all BILAG B scores improve to C/D at Week 36
and
○ No BILAG worsening in other body systems: no new BILAG A or ≥ 2 new BILAG B scores at Week 36
and
○ No worsening in SLEDAI-2K total score at Week 36 compared with baseline
and
○ No deterioration in PGA (< 10% worsening) on VAS 100 mm at Week 36 compared with baseline
and
○ No addition or increased dose level of anti-malarial drugs or immunosuppressive drugs or corticosteroids between Week 24 and Week 36 (this criterion will be identified by medical review)

Statistical Analysis Plan

Study Name: IFN-K-002

SAP version & date: v4, 18/Jun/2018

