4.1.2 Secondary efficacy endpoints

4.1.2.1 Clinical Secondary Endpoints

- Response to treatment with IFN-K, as measured by the SLE Responder Index (SRI)-4 response criteria at Week 36:
 - Reduction \geq 4 points in SELENA-SLEDAI at week 36 compared with baseline
and
 - No new BILAG A at Week 36
and
 - No more than 1 new BILAG B at Week 36
and
 - No deterioration at Week 36 in PGA (< 10% worsening) on VAS 100 mm compared with baseline
- Response to treatment with IFN-K, as measured by the composite SLE Responder Index (SRI)-4 response criteria at Week 36:
 - Same criteria as above
and
 - Sustained reduction in oral corticosteroids (\leq 5 mg and \leq 7.5mg/day) at Week 36 (these criteria will be identified by medical review)
- Response to treatment with IFN-K, as measured by SLEDAI response, defined as a reduction of the SLEDAI-2K score of at least 4 points at Week 36 compared to baseline
- Response to treatment with IFN-K, as measured by BILAG grade changes by body system
- Response to treatment with IFN-K, as measured by Incidence of SLE flare (SELENA SLEDAI flare index. BILAG flares)
- Response to treatment with IFN-K, as measured by SLICC/ACR-DI
- Response to treatment with IFN-K, as measured by Cutaneous LE Disease Area and Severity Index (CLASI)
- Response to treatment with IFN-K, as measured by LLDAS (Franklin *et al*, 2016)

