SAP version & date: v4, 18/Jun/2018

The BILAG global score will be defined as the summation of the numerical values for the nine-system scores as given by the following formula:

$$\text{Numerical global score (xs)} = A*12 + B*8 + C*1$$

Where A, B and C represent the number of Grades A, B and C respectively at each assessment. Grades D and E are considered as 0 (Chee-Seng Yee *et al*, 2010).

All BILAG data will be listed in Listing 16.2.6.3.

5.2.4.3.4 *SELENA SLEDAI flare index*

The numbers of patients with a mild or moderate, or severe SLE flare (SELENA-SLEDAI flare index) and corresponding number of SLE flare will be presented. (Statistical table 14.2.13).

The total score at each visit (planned in the protocol) and change from baseline by treatment group will also be presented. The change at Week 36 will be analyzed using a t-test. (Statistical tables 14.2.14.1 to 14.2.14.2).

All SELENA-SLEDAI flare index data will be listed in Listing 16.2.6.4.

5.2.4.3.5 *SLICC/ACR-DI*

Total score at each visit and change from baseline by treatment group will be presented. The change at Week 36 will be analyzed using a t-test. (Statistical tables 14.2.15.1 to 14.2.15.2).

All SLICC/ACR-DI data will be listed in Listing 16.2.6.5.

5.2.4.3.6 *CLASI*

Total activity score and Total damage score at each visit and change from baseline by treatment group will also be presented. The changes at Week 36 will be analyzed using a t-test. (Statistical tables 14.2.16.1 to 14.2.17.2).

All CLASI data will be listed in Listing 16.2.6.6.

5.2.4.3.7 *LLDAS*

Number of patients achieving a LLDAS at Week 36 will be presented by treatment group (Statistical table 14.2.18). It is defined as:

- SLEDAI-2K ≤ 4 , with no activity in major organ systems (renal, CNS, cardiopulmonary, vasculitis, fever) and no haemolytic anaemia or gastrointestinal activity
- No new features of lupus disease activity compared with the previous assessment (New feature is defined as any BILAG item recorded as "new" (modality 4) at Week 36)
- Physician global assessment (PGA, scale 0–3) ≤ 1
- Current prednisolone (or equivalent) dose ≤ 7.5 mg daily (this criterion will be identified by medical review)
- Well tolerated standard maintenance doses of immunosuppressive drugs and approved biological agents, excluding investigational drugs (this criterion will be identified by medical review)

Statistical Analysis Plan

Study Name: IFN-K-002

SAP version & date: v4, 18/Jun/2018

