7.5 LLDAS

Analysis for LLDAS, initially not planned in the protocol, will be done.

8 Software documentation

All summaries and statistical analyses will be generated using SAS version 9.4 or higher.

Statistical Analysis Plan

Study Name: IFN-K-002

SAP version & date: v4, 18/Jun/2018

9 Derived data

Derived variable	Derivation algorithm
Change from baseline to visit V (continuous)	
Change from baseline of variable X=X(Visit V)-X(Baseline)
 
 ○ Negative values indicate a decrease in X ○ Positive values indicate an increase in X
Percent change from baseline to visit V (continuous)	
Percent change from baseline of variable X=100 *[X(Visit V)-X(Baseline)]/X(Baseline)
 
 ○ Negative values indicate a decrease in X ○ Positive values indicate an increase in X
Treatment Compliance (continuous)	
The compliance Ci for patient i will be computed according to:
 $C_i = \frac{D_i^t * 100}{D_i^p}$ 
where D_i^p mg is the total amount (mg) of IP prescribed to patient i and D_i^t is the total amount (mg) of IP actually taken by the patient during the study i.e., before the end of study for patient i.

Treatment compliance (categorical) (if relevant)	
Categorial variable with three modalities:
 
 • $C_i < 80\%$ • $80\% \leq C_i < 120\%$ • $C_i \geq 120\%$
Event Duration	$(\text{End Date}) - (\text{Start Date}) + 1$
BILAG score	See BILAG-2004 Index scoring
SLEDAI-2K and SELENA SLEDAI	Sum of the weights
SLICC/ACR	Sum of items
CLASI	Sum of items
FACIT	See FACIT-Fatigue Subscale Scoring Guidelines (Version 4)

Statistical Analysis Plan

Study Name: IFN-K-002

SAP version & date: v4, 18/Jun/2018

Derived variable	Derivation algorithm
SF-36	See SF-36 Health Survey, Manual and Interpretation Guide
Time to event SLE flare	
SLE flare will be identified in BILAG-2004 scoring.
 
SLE flares are predefined as a BILAG A or B score due to items that were new or worse in any of the eight organ system (Isenberg et Al).
 
For patient with a SLE flare: Time to event = Visit date of corresponding BILAG – Date of Week 0 + 1
 
For patient without SLE flare: Time to event = Date of Week 36 (or date of end of study for patients prematurely withdrawn before Week 36) – Date of Week 0 +1

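### Does LLDAS become unusable because its PGA criterion is on a 0–3 scale while PGA is recorded on a 100 mm VAS, and is the 10% PGA condition in BICLA and SRI-4 left undefined?

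*SAP*

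**What the plan says.** **Scale.** Protocol 11.6 states: "PGA score is captured using 100 mm VAS". The SAP uses the same variable elsewhere. Its per-protocol definition (3.3.2), for instance, excludes patients for, among other reasons, "or missing PGA on VAS 100 mm at week 36".

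**LLDAS.** SAP 4.1.2.1 lists among the clinical secondary endpoints "Response to treatment with IFN-K, as measured by LLDAS" and cites a published definition. SAP 7.5 records that it was added after the protocol: "Analysis for LLDAS, initially not planned in the protocol, will be done". SAP 5.2.4.3.7 gives five criteria at Week 36, one of which is "Physician global assessment (PGA, scale 0–3) ≤ 1". The prednisolone and immunosuppressant criteria are marked for medical review; the PGA criterion is not. The derived-data table in SAP section 9 has no row for PGA or LLDAS.

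**The 10% condition.** BICLA (SAP 4.1.1) requires "No deterioration in PGA (< 10% worsening) on VAS 100 mm at Week 36 compared with baseline". SRI-4 (SAP 4.1.2.1) requires "No deterioration at Week 36 in PGA (< 10% worsening) on VAS 100 mm compared with baseline", and the composite SRI-4 inherits it. Neither cites section 9, which defines percent change from baseline generically as 100 times the visit value minus baseline, divided by baseline.

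**The concern.** The LLDAS threshold and the collected variable are on different scales. Applied literally to the VAS, a limit of 1 would mean 1 mm, which almost no patient with lupus would meet. Applied after conversion, it would mean roughly a third of the scale. The Week 36 count by arm therefore seems to depend on a choice the SAP does not make, and the protocol cannot supply it because LLDAS is not in the protocol.

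The 10% condition looks more serious because it is part of a co-primary endpoint. Two programmers could read it differently, one as 10% of the patient's own baseline and the other as 10 mm of the 100 mm scale. They could then classify the same patient differently on BICLA and SRI-4. SAP 5.2.4.1 also describes the BICLA result by the size of the observed difference (10% marginal, 15% important) whatever the p-value, so responder status feeds directly into how the trial is described.

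**Working it through.** No sample size, power or error rate in the documents depends on the PGA scale, so there is no stated figure to reproduce. The check is whether an analyst can get from the text to a rule, and how far apart the candidate rules lie.

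**LLDAS cut-off.** Inputs: limit 1 on 0–3 (SAP 5.2.4.3.7); VAS length 100 mm (Protocol 11.6). Assumption: linear rescaling with matching end points.

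- Rescaled cut-off: 100 × 1/3 = 33.3 mm.
- Literal reading on the VAS: 1 mm, which is 3 × 1/100 = 0.03 on 0–3. The criterion states that its scale is 0–3, so this reading contradicts its own text.

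**Could a 0–3 PGA also be recorded?** The SELENA-SLEDAI flare form (Protocol Appendix 4) sets PGA thresholds of a rise of 1.0 or more and a level of 2.5. These suit a short scale, not 0–100 mm. The form is completed at Week 36 (Protocol 10.9.12), the LLDAS visit. The appendix does not name the scale, and the case report form is not among the documents, so this is a possibility, not a finding. It does mean that one cannot say a 0–3 value is not collected.

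**The 10% condition.** Let B be the baseline PGA in mm.

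- Relative reading (section 9 formula): fails at Week 36 ≥ 1.1 × B.
- Full-scale reading: fails at Week 36 ≥ B + 10.
- Width of disagreement: (B + 10) − 1.1 × B = 10 − 0.1 × B, as long as both limits lie within 100 mm.

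| Baseline B (mm) | Relative: fails at | Full scale: fails at | Disagreement (mm) |
|---|---|---|---|
| 20 | 22 | 30 | 8 |
| 40 | 44 | 50 | 6 |
| 60 | 66 | 70 | 4 |
| 80 | 88 | 90 | 2 |
| 90 | 99 | 100 | 1 |
| 95 | 104.5 (off scale) | 105 (off scale) | 0 |

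The relative reading is the stricter one over most of the range, but not all of it. Above 100/1.1 = 90.9 mm neither limit can be reached and the readings agree. At B = 0 the relative percentage is undefined. Patients enter with SLEDAI of at least 6 and at least one BILAG A or two BILAG B scores (Protocol 8.3.1), so a baseline PGA of 0 should be rare.

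**Which reading does the text favour?** The condition is a percentage worsening against baseline, and section 9 holds the SAP's only percent-change formula. That the condition does not cite section 9 says little. The first co-primary endpoint is itself a percent change from baseline, and SAP 5.2.4.1 does not cite section 9 for that formula either; its reference there concerns ethnic origin. The mention of the 100 mm VAS most naturally identifies the instrument.

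**Who is affected?** On BICLA, the reading matters only for a patient who meets every other component (BILAG improvement, no new BILAG activity, no SLEDAI-2K worsening, no treatment escalation) and whose PGA has nevertheless risen into the band above. With 80 evaluable patients per arm, each reclassified patient moves the difference by 1/80 = 1.25 points. The documents give no PGA distribution, so the number of such patients cannot be calculated.

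**The case for a change.** The best argument for changing the plan is that responder definitions should be fixed before unblinding and the cost is a few sentences. The 10% condition enters a co-primary endpoint that is labelled by observed size. SRI-4 carries more than its rank suggests, since SAP 5.2.4.3.1 says it could become the primary endpoint for further development. SAP 5.3.6 acknowledges that some investigators may have had access to unblinded information, which is a reason to leave little open. Section 9 is generic and gives no rule for a zero baseline.

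Part of this stands. The SAP does not name the PGA source for LLDAS, does not link the 10% condition to section 9, and says nothing on a baseline of 0. A note on each would do no harm. The argument does not show that either reading of the 10% condition is wrong, that the choice would favour one arm, or that a response rate would move materially. Writing 33.3 mm into the SAP has a drawback of its own. The documents neither support nor refute linearity, and if the flare page does hold a 0–3 PGA, an assumed conversion would displace a directly recorded value. Once section 9 is applied, repeating BICLA and SRI-4 under the other reading is a matter of preference.

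**Conclusion.** No change to the plan follows. These are omissions that analysts can fill sensibly from what is already written.

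- **LLDAS:** the criterion states its scale, so the choice is between a 0–3 value, if one is recorded, and a rescaled VAS (33.3 mm under linearity). The result is a descriptive count (Table 14.2.18) with no test and no role in deciding whether the study is positive.
- **10% condition:** section 9 gives a workable default, the patient's own baseline. The two readings differ by 8 mm at most for baselines from 20 mm up and coincide above about 90.9 mm. The effect on BICLA and SRI-4 is probably small, though it cannot be quantified, and no change in the 10% or 15% label is claimed.

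This rests on one rule being applied to both arms and settled before the blind is broken, in line with the SAP's statement in section 1 that it is validated before database lock and unblinding. It also rests on zero baselines being rare in a population selected for active disease. The source variable, the denominator and the zero-baseline convention can be recorded in the programming specification.

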5.2.4.4 Immunogenicity analysis

The following analysis will be performed on the PP population.

5.2.4.4.1 *Anti-IFN α binding antibody titers.*

- The number of patients with a positive antibody response over time (seropositivity) will be analyzed using frequency table methods (Statistical table 14.2.19). The definitions are the followings:
 - Seropositivity: A positive result (seropositivity) is defined when titer was ≥ 400 dil-1 and a negative result when titer is < 400 dil-1.
- Descriptive analysis will be done on Log-transformed dilution titers for anti-IFN α binding antibodies expressed as dilution factors at each time point. (Statistical table 14.2.20)
- Reverse cumulative distribution curves will be generated using anti-IFN α antibody titers (Statistical figure 14.2.2)
- GMT for anti-IFN α binding antibodies will be presented. Results will be expressed with 95% CI (Statistical table 14.2.21).

All corresponding data will be listed in Listing 16.2.6.7.

5.2.4.4.2 *Anti-IFN α antibody neutralizing capacity (NC50).*

- The number of patients with a positive antibody response over time (seropositivity) will be analyzed using frequency table methods (Statistical table 14.2.22). The definitions are the followings:
 - Seropositivity: A positive result (seropositivity) is defined when NC50 was ≥ 200 dil-1 and a negative result when NC50 is < 200 dil-1.
- Descriptive analysis will be done on Log-transformed NC50 for anti-IFN α neutralizing antibodies expressed as dilution factors at each time point (Statistical table 14.2.23)
- Reverse cumulative distribution curves will be generated using NC50 (Statistical figure 14.2.3)
- GMT for anti-IFN α neutralizing antibodies will be presented. Results will be expressed with 95% CI (Statistical table 14.2.24).

All corresponding data will be listed in Listing 16.2.6.8.

5.2.4.4.3 *Anti-KLH binding antibody titers.*

- The number of patients with a positive antibody response over time (seropositivity) will be analyzed using frequency table methods (Statistical table 14.2.25). The definitions are the followings:

Statistical Analysis Plan

Study Name: IFN-K-002

SAP version & date: v4, 18/Jun/2018

- Seropositivity: A positive result (seropositivity) is defined when titer was ≥ 400 dil-1 and a negative result when titer is <400 dil-1.
- Descriptive analysis will be done on Log-transformed dilution titers for anti-KLH binding antibodies expressed as dilution factors at each time (Statistical table 14.2.26)
- Reverse cumulative distribution curves will be generated using anti-KLH antibody titers (Statistical figure 14.2.14)
- GMT for anti- KLH binding antibodies will be presented. Results will be expressed with 95% CI (Statistical table 14.2.27).

All corresponding data will be listed in Listing 16.2.6.9.

5.2.4.5 Exploratory analyses

The following analysis will be performed on the FAS population except if otherwise specified.

5.2.4.5.1 **PGA scores**

PGA score at each visit and change from baseline by treatment group will be presented. (Statistical tables 14.2.28.1 to 14.2.28.2)

All PGA data will be listed in Listing 16.2.6.10.

5.2.4.5.2 **SLE flares**

Time to first SLE flare in patients will be analyzed using a cox regression model.

The first model will be adjusted on treatment group.

The second model will be performed only on patients IFN-K treated and will be adjusted on presence/absence of neutralizing antibodies. (Statistical tables 14.2.29.1 to 14.2.29.2)

5.2.4.5.3 **28-Tender and Swollen Joint Counts (SJC)**

28-Tender and Swollen Joint Counts and Joint Pain VAS at each visit and change from baseline will be presented. The changes at Week 36 will be analyzed using a t-test. (Statistical tables 14.2.30.1 to 14.2.32.2).

28-Tender and Swollen joint counts data will be listed in Listing 16.2.6.11, and joint Pain VAS data in Listing 16.2.6.12.

5.2.4.5.4 **Treatment failure**

- Proportion of treatment failure will be analyzed using frequency table methods. Patients will be considered as treatment failure if they receive more than 5 mg prednisone equivalent/day at any time between Week 24 (Visit 9) and Week 36 (Visit 12) or if their CS dose is increased above the Week 24 level is recorded (this criterion will be identified by medical review) (Statistical table 14.2.33)

5.2.4.5.5 **SF-36**

Statistical Analysis Plan

Study Name: IFN-K-002

SAP version & date: v4, 18/Jun/2018

Physical Component Summary (PCS) and Mental Component Summary (MCS) scores at each visit and change from baseline will be presented. The changes at Week 36 will be analyzed using a non-parametric Wilcoxon rank sum test (Statistical tables 14.2.34.1 to 14.2.35.2). If one is statistically significant then the individual domain scores will also be described.

In addition, number of patients with clinically meaningful improvements \geq Minimum Clinically Important Differences (MCID) of 2.5 points for summary and 5.0 points for domain scores between baseline and Week 36 will be presented. (Statistical tables 14.2.36 to 14.2.37)

All SF-36 data will be presented in Listing 16.2.6.13.

5.2.4.5.6 **FACIT**

Total scores at each visit and change from baseline by treatment group will be presented. The change at Week 36 will be analyzed using a t-test. (Statistical tables 14.2.39.1 to 14.2.39.2)

All FACIT data will be presented in Listing 16.2.6.14.

5.2.4.5.7 **Autoantibodies**

The levels of auto-antibodies (ANA, anti-dsDNA, anti-Smith antigen [anti-Sm], anti-RNP, anti-SSA/Ro, anti-SSB/La, anti-cardiolipin, and anti- β 2-glycoprotein I antibodies) will be described at each visit by treatment group. Change from baseline by treatment group will be presented for quantitative parameters. For anti-dsDNA, the change at Week 36 will be analyzed using a t-test. (Statistical tables 14.2.40.1 to 14.2.40.2). These analyses will be performed on the PP population.

All auto-antibodies data will be listed in Listing 16.2.6.15.

5.2.4.5.8 **Biomarkers**

The biomarkers (C3, C4, CH50) at each visit and change from baseline by treatment group will be presented. (Statistical tables 14.2.41.1 to 14.2.41.2). For C3 the change at Week 36 will be analyzed using a t-test. These analyses will be performed on the PP population.

All biomarkers data will be listed in Listing 16.2.6.16.

5.2.4.5.9 **Anti-IFN α and anti-KLH antibody isotyping**

Descriptive analysis will be performed on Anti-IFN α and anti-KLH antibody isotyping data. (Statistical table 14.2.42)

All corresponding data will be listed in Listing 16.2.6.17.

5.2.4.5.10 **Anti-Hemagglutinin antibody response following influenza vaccination**

Seroconversion (four folds increase in antibody titers post-vaccination) and seroprotection (HIA antibody titers \geq 1:40 post-vaccination) will be presented by treatment group for each visit. In addition, results by visit will be presented according to status of anti-IFN α neutralizing antibodies (positive/negative) at the corresponding visit (Statistical table 14.2.43). These analyses will be performed on the FAS population, only on patients vaccinated with seasonal Flu and with sample at baseline and post-baseline.

Statistical Analysis Plan

Study Name: IFN-K-002

SAP version & date: v4, 18/Jun/2018

All corresponding data will be listed in Listing 16.2.6.18.

5.2.4.5.11 ***Neutralizing Anti-IFN α antibodies towards IFN α subtypes***

Descriptive analysis will be performed on Neutralizing Anti-IFN α antibodies towards IFN α subtypes data. (Statistical table 14.2.44)

All corresponding data will be listed in Listing 16.2.6.19.

5.2.4.5.12 ***Other***

IFN β and IFN ω cross neutralization data will be provided in Listing 16.2.6.20

5.2.4.5.13 ***Correlation***

Correlation between immunogenicity responses (Anti-IFN α binding positive / neutralizing antibodies positive vs anti-IFN α binding positive / neutralizing antibodies negative) and clinical parameters (BICLA & SRI-4); between clinical and biological parameters (IFN gene signature, C3, dsDNA, ANA), and between immunogenicity responses and biological parameters will be presented on the PP population. The following analyses will be performed:

- Qualitative description for clinical parameters at V12 by status (positive/negative) of anti IFN α neutralizing antibodies at V12 on patients treated with IFN-K and with positive anti IFN α binding antibodies at V12
- Quantitative or qualitative description for biological parameters at V12 by treatment group on patients responder for BICLA at V12
- Quantitative or qualitative description for biological parameters at V12 by treatment group on patients non responder for BICLA at V12
- Quantitative or qualitative description for biological parameters at V12 by treatment group on patients responder for SRI4 at V12
- Quantitative or qualitative description for biological parameters at V12 by treatment group on patients non responder for SRI4 at V12
- Quantitative or qualitative description for biological parameters at V12 by status (positive/negative) of anti IFN α neutralizing antibodies at V12 on patients treated with IFN-K and with positive anti IFN α binding antibodies at V12

(Statistical Tables 14.2.45.1 to 14.2.45.6)

